## 8.7. Vital Signs and Physical Evaluations

Vital sign measurements including systolic and diastolic blood pressure (mmHg), temperature (°C), pulse (beats/min) and respiratory rate (breaths/minute) will be assessed at each visit, including change from pre-first vaccination and pre-second vaccination ([Table 69](#) through [Table 80](#)). Vital signs will be tabulated by visit and vaccination group, including mean, standard deviation, median and range. A full listing will be prepared ([Listing 10](#), Appendix 3) and will include study visit, value, units and change from baseline.

Physical exam results, including number and proportion of participants with abnormalities, will be summarized for the safety analysis population and presented in [Appendix 1.H. \(Table 81](#) through [Table 89\)](#), by vaccination group. A full listing will be prepared ([Listing 12](#), Appendix 3).

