**Table 1: Treatment Groups - Protocol Table 3 (see [Table 1](#) in Section [4.1.](#))**

**Table 2: Phase 1 Dose Escalation Step – Protocol Table 4 (see [Table 2](#) in Section [4.1.](#))**

**Table 3: Schedule of Study Visits and Procedures – Protocol Table 5**

VISIT	Screen	V1	V2	V3	V4	V5	V6	V7
Study Day (allowed window in days)	-42 to 1	1	8 (+3)	29 (+3)	36 (+3)	43 (+3)	57 (+7)	197 (+14)
Informed consent	✓							
Demographics	✓							
Medical History	✓							
Concomitant medications A	✓	✓	✓	✓	✓	✓	✓	✓
Eligibility check	✓			~				
Vital signs	✓	✓ ^ ✓	✓	✓ ^ ✓	✓	✓	✓	✓
Complete physical exam	✓							
Targeted physical exam B		✓	✓	✓	✓	✓	✓	✓
Clinical chemistry C	✓		✓		✓			
Hematology D	✓		✓		✓			
Viral serology tests E	✓							
Urine pregnancy test F	✓	✓ ^ ✓		✓				
Unsolicited AEs G	✓	✓	✓	✓	✓	✓	✓	✓
Concomitant medications H	✓		✓	✓	✓	✓	✓	✓
Randomization		✓		~				
Blood for humoral immunity		✓		✓		✓		✓
Blood for CMI I		✓				✓		✓
Administer study product		✓		✓				
Observation/solicited AEs		✓		✓				
Provide Diary Card		✓		✓				
Review Diary Card			✓		✓			
Exit study								
Blood volumes (mL):								
Safety laboratory tests (Phase 1 only)	4		4		4			
HBV and HCV screening	2		0		0			
Humoral immunity		10		10		10		10
Cell-mediated immunity		16				16		16

~ Confirmation

A Evaluations will be conducted twice – before and after vaccinationB After Visit 6, only medications associated with an AESI, MAAE or SAE will be recorded.C Targeted PE will be conducted only in the event of new symptom, sign or, until Visit 6, any new AE; or, after Visit 6, any new AESI, MAAE or SAE.D Serum creatinine, ALT, AST, total bilirubin; only in Phase 1.E WBC count, hemoglobin, platelets; only in Phase 1.F HBsAg, HCV AbG Women of childbearing potential (WOCBP) onlyH After Visit 6, only AESI, MAAEs, and SAEs will be recorded.I After Visit 6, only concomitant medications associated with a newly reported AESI, MAAE or SAE will be recorded Only in subset of subjects in Phase 2

Remark: 1 month = 28 days (4 weeks)

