## Appendix 1.G. Vital Signs

**Table 69: Overall Number of Subject with Abnormal of Vital Sign result at Post -First Vaccination**

	All (N = 120)	1 µg (N = 25)	3 µg (N = 25)	10 µg (N = 25)	1 µg + CpG (N = 25)	Placebo (N = 20)
Overall, n (%)						
Systolic Blood Pressure (mmHg)	xx (xx.x%)	xx (xx.x%)	xx (xx.x%)	xx (xx.x%)	xx (xx.x%)	xx (xx.x%)
Diastolic Blood Pressure (mmHg)	xx (xx.x%)	xx (xx.x%)	xx (xx.x%)	xx (xx.x%)	xx (xx.x%)	xx (xx.x%)
Pulse (Beats/min)	xx (xx.x%)	xx (xx.x%)	xx (xx.x%)	xx (xx.x%)	xx (xx.x%)	xx (xx.x%)
Respiratory Rate (Breaths/min)	xx (xx.x%)	xx (xx.x%)	xx (xx.x%)	xx (xx.x%)	xx (xx.x%)	xx (xx.x%)
Temperature (°C)	xx (xx.x%)	xx (xx.x%)	xx (xx.x%)	xx (xx.x%)	xx (xx.x%)	xx (xx.x%)
with one or more abnormal result	xx (xx.x%)	xx (xx.x%)	xx (xx.x%)	xx (xx.x%)	xx (xx.x%)	xx (xx.x%)
with no abnormal result	xx (xx.x%)	xx (xx.x%)	xx (xx.x%)	xx (xx.x%)	xx (xx.x%)	xx (xx.x%)
Post-first vaccination						
Systolic Blood Pressure (mmHg)						
Diastolic Blood Pressure (mmHg)						
Pulse (Beats/min)						
Respiratory Rate (Breaths/min)						
Temperature (°C)						
with one or more abnormal result						
with no abnormal result						
Visit 2 (Day 8)						
Systolic Blood Pressure (mmHg)						
Diastolic Blood Pressure (mmHg)						
Pulse (Beats/min)						
Respiratory Rate (Breaths/min)						
Temperature (°C)						
with one or more abnormal result						
with no abnormal result						

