**Table 70: Overall Number of Subject with Abnormal of Vital Sign at Post- Second Vaccination**

	All (N = 120)	COVIVAC				Placebo (N = 20)
		1 µg (N = 25)	3 µg (N = 25)	10 µg (N = 25)	1 µg + CpG (N = 25)	
Overall, n (%)						
Systolic Blood Pressure (mmHg)	xx (xx.x%)	xx (xx.x%)	xx (xx.x%)	xx (xx.x%)	xx (xx.x%)	xx (xx.x%)
Diastolic Blood Pressure (mmHg)	xx (xx.x%)	xx (xx.x%)	xx (xx.x%)	xx (xx.x%)	xx (xx.x%)	xx (xx.x%)
Pulse (Beats/min)	xx (xx.x%)	xx (xx.x%)	xx (xx.x%)	xx (xx.x%)	xx (xx.x%)	xx (xx.x%)
Respiratory Rate (Breaths/min)	xx (xx.x%)	xx (xx.x%)	xx (xx.x%)	xx (xx.x%)	xx (xx.x%)	xx (xx.x%)
Temperature (°C)	xx (xx.x%)	xx (xx.x%)	xx (xx.x%)	xx (xx.x%)	xx (xx.x%)	xx (xx.x%)
with one or more abnormal result	xx (xx.x%)	xx (xx.x%)	xx (xx.x%)	xx (xx.x%)	xx (xx.x%)	xx (xx.x%)
with no abnormal result	xx (xx.x%)	xx (xx.x%)	xx (xx.x%)	xx (xx.x%)	xx (xx.x%)	xx (xx.x%)
Post-second vaccination						
Systolic Blood Pressure (mmHg)						
Diastolic Blood Pressure (mmHg)						
Pulse (Beats/min)						
Respiratory Rate (Breaths/min)						
Temperature (°C)						
with one or more abnormal result						
with no abnormal result						
Visit 4 (Day 36)						
Systolic Blood Pressure (mmHg)						
Diastolic Blood Pressure (mmHg)						
Pulse (Beats/min)						
Respiratory Rate (Breaths/min)						
Temperature (°C)						
with one or more abnormal result						
with no abnormal result						
Visit 5 (Day 43)						
Systolic Blood Pressure (mmHg)						
Diastolic Blood Pressure (mmHg)						
Pulse (Beats/min)						
Respiratory Rate (Breaths/min)						
Temperature (°C)						

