**Table 72: Systolic Blood Pressure (mmHg) Post-second Vaccination Compared to Pre-second Vaccination**

	All	COVIVAC				Placebo (N = 20)
		1 µg (N = 25)	3 µg (N = 25)	10 µg (N = 25)	1 µg + CpG (N = 25)	
Pre-second vaccination						
n	xx	xx	xx	xx	xx	xx
Mean (SD)	xx.xx (xx.xx)	xx.xx (xx.xx)	xx.xx (xx.xx)	xx.xx (xx.xx)	xx.xx (xx.xx)	xx.xx (xx.xx)
Median (q1-q3)	xx (xx-xx)	xx (xx-xx)	xx (xx-xx)	xx (xx-xx)	xx (xx-xx)	xx (xx-xx)
Min-Max	xx-xx	xx-xx	xx-xx	xx-xx	xx-xx	xx-xx
Post-second vaccination						
n	xx	xx	xx	xx	xx	xx
Mean (SD)	xx.xx (xx.xx)	xx.xx (xx.xx)	xx.xx (xx.xx)	xx.xx (xx.xx)	xx.xx (xx.xx)	xx.xx (xx.xx)
Median (q1-q3)	xx (xx-xx)	xx (xx-xx)	xx (xx-xx)	xx (xx-xx)	xx (xx-xx)	xx (xx-xx)
Min-Max	xx-xx	xx-xx	xx-xx	xx-xx	xx-xx	xx-xx

\*p-value =

Normal

Abnormal

Mild

Moderate

Severe

Potentially life threatening

\*p-value =

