## Appendix 1.H. Physical Examinations

**Table 81: Overall Number of Subject with Abnormal of Any Physical Examination Result Post -First Vaccination**

	All (N = 120)	COVIVAC				Placebo (N = 20)
		1 µg (N = 25)	3 µg (N = 25)	10 µg (N = 25)	1 µg + CpG (N = 25)	
Visit 2 (Day 8)						
General Appearance						
HEENT						
Cardiovascular						
Respiratory						
Abdomen						
Musculoskeletal						
Extremity/Skin						
Neurological						
Lymph Nodes						
with one or more abnormal result						
with no abnormal result						

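### The Day 29 pre-second-dose vital-sign reading, which is the 28-day follow-up of dose 1, enters no abnormality or grade count and serves only as the dose-2 reference

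*SAP*

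**What the plan says.** Section 8.7 states that vital signs "will be assessed at each visit, including change from pre-first vaccination and pre-second vaccination". It adds: "Vital signs will be tabulated by visit and vaccination group, including mean, standard deviation, median and range".

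The schedule (Appendix 1.A, Table 3) has vital signs at every visit. At Visits 1 and 3 they are taken twice; the footnote reads "Evaluations will be conducted twice – before and after vaccination". Section 4.1 lists Visit 3 among the safety assessments, as the visit 28 days after the first vaccination.

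The abnormality counts are in Table 69, "Overall Number of Subject with Abnormal of Vital Sign result at Post -First Vaccination", and Table 70, "Overall Number of Subject with Abnormal of Vital Sign at Post- Second Vaccination". Changes by parameter are in Tables 71, 73, 75, 77 and 79 for dose 1, and in Tables 72, 74, 76, 78 and 80 for dose 2; Table 72, for example, is "Systolic Blood Pressure (mmHg) Post-second Vaccination Compared to Pre-second Vaccination".

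For physical examinations, Table 81 is "Overall Number of Subject with Abnormal of Any Physical Examination Result Post -First Vaccination", Table 82 is its post-second-dose counterpart, and Tables 83 to 89 give results visit by visit.

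**The concern.** The Day 29 pre-dose reading is the last vital-sign assessment that can reflect dose 1 alone. If it is counted under neither dose, the Overall block for dose 1 is incomplete by one scheduled reading. A change that emerged after Day 8 would also be absorbed into the reference against which dose 2 is judged.

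The two doses are not treated alike. The 28-day follow-up of dose 2 (Day 57) is counted in Table 70, so the Overall figures for the two doses rest on different follow-up. Safety and tolerability after each dose is the primary objective of Phase 1, so the final report should describe dose 1 with all the readings taken for it.

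**Working it through.** The plan gives no figure to reproduce. The check sets the shells against the schedule, followed by a short calculation of the possible size.

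**Step 1. Vital-sign readings after dose 1 and before dose 2.** Table 3 gives three: immediately after dose 1, Day 8, and Day 29 before dose 2.

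**Step 2. Where each is counted as normal or abnormal.**

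| Reading | Table 69 | Table 70 | Tables 71, 73, 75, 77, 79 | Tables 72, 74, 76, 78, 80 |
|---|---|---|---|---|
| Immediately after dose 1 | yes | no | yes, graded | no |
| Day 8 | yes | no | yes, graded | no |
| Day 29 before dose 2 | no | no | no | reference only: n, mean, median, range |

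Table 69 therefore covers 2 of 3 readings. The third has Normal/Abnormal or grade rows in no table, and none compares it with pre-first vaccination. The haematology shells (Tables 61 to 63), by contrast, show Normal/Abnormal and grades for the baseline value.

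**Step 3. What the paired test does.** The footnotes to the dose-2 tables apply a McNemar test to Normal/Abnormal status, comparing the pre-vaccination value with each follow-up. For dose 2 the pre-vaccination value is the Day 29 reading, so the test needs a status that the tables never display.
- Abnormal at Day 29 and still abnormal later: a concordant pair, which adds nothing to the test. The subject is nevertheless counted in Table 70 as abnormal after dose 2.
- Abnormal at Day 29 only: in neither Table 69 nor Table 70. In the test this subject is a change from abnormal to normal.

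**Step 4. Size of the shortfall in the Overall post-dose-1 rate.** The relative shortfall is the share of subjects with any post-dose-1 abnormality whose only abnormal reading is Day 29. The documents give no rates, so p, the chance of an abnormal reading per parameter and visit, is an assumption.
- Every abnormality already present by Day 8: no subject is abnormal at Day 29 alone, and the shortfall is 0%.
- Independent visits with equal p: the tabulated rate is 1 − (1 − p)², and the rate with Day 29 included is 1 − (1 − p)³.

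| p | As tabulated | With Day 29 | Ratio | Relative shortfall |
|---|---|---|---|---|
| 0.02 | 0.0396 | 0.0588 | 0.67 | 33% |
| 0.05 | 0.0975 | 0.1426 | 0.68 | 32% |
| 0.10 | 0.190 | 0.271 | 0.70 | 30% |

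**Step 5. Physical examinations.** Table 81 covers Day 8 only, and Table 82 covers Days 36, 43, 57 and 197, so neither summary includes Day 29. Table 85 does tabulate Day 29 as normal, abnormal, clinically significant or not done, by body system and group. No examination table uses a dose-2 reference or a paired test.

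**The case against.** Several points on the other side stand.

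- Section 8.7 promises summary statistics by visit, and the Day 29 pre-dose value gets them in Tables 72, 74, 76, 78 and 80. For vital signs the section promises no abnormality count at every visit. Using the immediate pre-dose value as the reference for dose 2 is stated in the text and defensible. The weakness is that this is the value's only use, although 8.7 also calls for change from pre-first vaccination.
- Individual Day 29 values appear in Listing 10. The adverse event definition in section 3.3.1 is broad enough to take in a relevant vital-sign change, and the note to section 4.2.3 has clinically relevant abnormal vital signs reassessed at both vaccination visits. These limit the clinical risk but produce no count. Section 3.3.3, on recording clinically significant findings as adverse events, names examination and laboratory findings, not vital signs.
- The omission is the same in all groups, placebo included, and no bias between groups is shown.
- Vital signs are not among the primary endpoints in section 3.2.1, and Tables 69 to 89 are not in the interim report list in section 6.6.1.

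A reader might also infer three stronger things that the document does not support.

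- That Day 29 examination abnormalities go uncounted and become a dose-2 baseline. Table 85 counts them, and the examination tables make no baseline comparison. Targeted examinations are also event-driven: "Targeted PE will be conducted only in the event of new symptom, sign or, until Visit 6, any new AE".
- That a vital-sign abnormality starting between Day 8 and Day 29 and persisting is never counted. Table 70 counts it at each later reading where it remains. The fault is attribution to dose 2, not loss.
- That the post-dose-1 rate is understated by 30–33%. That figure needs independent visits, whereas repeated blood pressure or pulse readings in one person are positively correlated.

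**Conclusion.** The point holds for vital signs. Two of the three post-dose-1 readings are counted; the Day 29 pre-dose reading is neither counted nor graded in any table and acts only as the dose-2 reference. This needs no assumption, since it follows from comparing the shells with the schedule.

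Its numerical effect does rest on assumptions. The shortfall in the Overall post-dose-1 rate is 0% if every abnormality is present by Day 8, and about one third under independent visits with equal rates of 2–10%. Positive correlation between visits pulls it towards the lower end. One third is not a mathematical ceiling, because abnormalities concentrated after Day 8 would give more, but nothing in the SAP suggests that pattern.

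For physical examinations the gap is confined to the two summary tables. The consequence is an incomplete and partly misattributed description of vital signs in the final report. Down-selection to Phase 2 is not affected through the listed interim tables. The correction should be made because it is specific and costs little.

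**What to change.** - Tables 71, 73, 75, 77 and 79: add a block for Visit 3 before the second vaccination (Day 29), with Normal/Abnormal, grades and change from pre-first vaccination.
- Table 69: add a Day 29 pre-dose block and include it in the Overall counts.
- Tables 72, 74, 76, 78 and 80: show Normal/Abnormal for the pre-second value, so that the starting status used in the McNemar test is visible.
- Table 81: add Visit 3.

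Change from pre-first vaccination for Days 36 to 197 would be a useful addition but is optional.

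The cost is limited to table shells and programming, because the readings are already scheduled at Visit 3. No visit, procedure or interim output changes.

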## 9. IMMUNOGENICITY

The analysis of immunogenicity will be performed on the per protocol population as the primary analysis and the full analysis population as a secondary analysis. Analyses described below will be summarized in the interim analyses for all subjects included in the first phase of the study. Relative endpoints derived from Geometric Mean Fold Rise (GMFR) will include all subjects from the per protocol population. Absolute endpoints such as those derived from the Geometric Mean Titer (GMT) will exclude baseline seropositive subjects (i.e., subjects with anti-S IgG antibody titer  $\geq$  LLOQ of the assay at baseline).

Immunogenicity data will be descriptively summarized including the mean, SD, median, range (min and max), GMT, and 95% CI for the GMT with one-half the lower limit of quantification (LLOQ) and with the upper limit of quantification (ULOQ) used as the observed value, whenever these limits are met. For estimation of the GMT, GMT ratio, and corresponding confidence limits, analyses will incorporate censoring where appropriate and log-scale coefficients will be back-transformed in order to compute the estimate and corresponding confidence limits for the relevant quantity. GMFRs will be computed using estimates of the log difference of the paired samples, with corresponding CIs computed via the *t*-distribution, utilizing the antilog transformation to present the ratio. Analyses of binary variables will include 95% CIs computed via the Clopper-Pearson method. Additionally, the distribution of the titers will be summarized using reverse cumulative distribution curves. ([Figure 27](#) through [Figure 32](#)).

The immunogenicity analysis part will be summarized in term of GMT ratio comparing between dose levels and dose with and without adjuvant. The comparing doses of GMT ratio (95% CI) will be performed for the following pairwise: (1) NDV-HXP-S 1  $\mu$ g vs. 3  $\mu$ g, (2) 1  $\mu$ g vs. 10  $\mu$ g, (3) 3  $\mu$ g vs. 10  $\mu$ g, (4) 1  $\mu$ g vs. 1  $\mu$ g+CPG, (5) 3  $\mu$ g vs. 1  $\mu$ g+CPG, (6) 10  $\mu$ g vs. 1  $\mu$ g+CPG.

### 9.1. NT50 and NT80 against SARS-CoV-2 Pseudovirus

The pseudovirus neutralization assay (PNA) will be used to quantify the functional humoral immune response against SARS-CoV-2 by measuring the 50% and 80% neutralizing titer (NT50 and NT80) against a SARS-CoV-2 pseudovirus.

The results generated from the central laboratory (NEXELIS, Canada) for SARS-CoV-2 PNA will be reported with titer units “NT50” and “NT80”. A correlation factor of 1/1.872 will be applied to convert the reported results from NT50 titer to IU/mL which is the assigned unit for WHO International Standard.

The following formula shall be used for converting NT50 titer to IU/mL:

$$\text{Result (IU/mL)} = \text{Result (NT}_{50} \text{ titer)} / 1.872$$

The NT50 and NT80 GMT against SARS-CoV-2 pseudovirus will be described along with its 95% CI at baseline (D1), 28 days after the first vaccination (D29), and 14 days (D43) and 6 months (D197) after the second vaccination in subjects who are anti-S IgG seronegative (i.e., anti-S IgG value less than LLOQ of the assay) at baseline ([Table 90](#), [Table 91](#), [Table 94](#), [Table 95](#), Appendix 1). The NT50 will also be described via the geometric mean concentration (GMC) in IU/mL along with its 95% CI at D1, D29, D43 and D197.

The GMT ratio with 95% CI for pairwise comparison of NT50 and NT80 GMT values between dose levels and dose with and without adjuvant will be presented at 28 days after the first vaccination, and 14 days, 6 months and 12 months after the second vaccination for each pair ([Table 92](#), [Table 93](#), [Table 96](#), [Table 97](#)).

The GMFR from baseline in NT50 and NT80 against SARS-CoV-2 pseudovirus at 28 days after the first vaccination, and 14 days, 6 months and 12 months after the second vaccination will be calculated along with its 95% CI for each study group ([Table 98](#) through [Table 101](#), Appendix 1).

Number and percentage (with 95% CI) of subjects with NT50 and NT80 seroresponses against SARS-CoV-2 pseudovirus as defined by (1) a  $\geq$  4-fold increase from baseline, and (2) a  $\geq$  10-fold increase from baseline at 28 days after the first vaccination, and 14 days, 6 months and 12 months after the second vaccination will be summarized at each time point for each study group ([Table 102](#) through [Table 109](#), Appendix 1).

## 9.2. Anti-S IgG Assessed by ELISA

Anti-S IgG antibody titers will be measured by ELISA assay which detects IgG antibodies to the full-length pre-fusion Spike protein of SARS-CoV-2.

Serum antibody concentration will be reported from the central laboratory (NEXELIS, Canada) in ELISA Units (ELU)/mL. A correlation factor of 1/7.9815 will be applied to convert the reported results from ELU/mL to Binding Antibody Units (BAU)/mL which is the assigned unit for WHO International Standard.

The following formula shall be used for converting concentration units from ELU/mL to BAU/mL:

$$\text{Result (BAU/mL)} = \text{Result (ELU/mL)} / 7.9815$$

Anti-S IgG antibody results will be summarized at baseline, 28 days after the first vaccination, and 14 days, 6 months and 12 months after the second study injection. The summarization of the anti-S IgG antibody titers will be performed for the overall and by study group at each time point.

The summarization will include GMTs with 95% CIs, including baseline ([Table 110](#), [Table 111](#), Appendix 1), GMT ratio with 95% CI for pairwise comparison between vaccine groups ([Table 112](#), [Table 118](#), Appendix 1), GMFR from baseline with 95% CI ([Table 114](#), [Table 115](#), Appendix 1), and percent of subjects with  $\geq$  4-fold and  $\geq$  10-fold increase in the anti-S IgG antibody titers compared with baseline ([Table 116](#) through [Table 119](#), Appendix 1).

## 10. REPORTING CONVENTIONS

P-values will be reported to 3 decimal places; p-values less than 0.001 will be reported as “<0.001” and p-values greater than 0.999 will be reported as “>0.999”. Means and medians will be presented to one decimal place more than the raw value, standard deviations and confidence intervals will be presented to 2 extra decimals. Percentages will be reported to one decimal and corresponding 95% CIs will be to two decimals. Percentages less than 0.1% (or <0.01%) will be reported as “<0.1” (or “<0.01”), percentages >99.9% (or >99.99%) will be reported as “>99.9” (“>99.99”) and 100% will be reported as “100”.

## 11. TECHNICAL DETAILS

SAS version 9.4 will be used to generate all tables, figures and listings.

## 12. SUMMARY OF CHANGES IN THE CONDUCT OF THE STUDY OR PLANNED ANALYSES

For SARS-CoV-2 PNA, NT50 and NT80 will be determined based on the dilution of serum required to achieve 50% and 80% reduction in relative luminescence units (RLU) value compared to pseudoparticle control. The results generated from the central laboratory will be reported with titer units “NT50” and “NT80”. In order to convert the reported values from the laboratory to be according to the WHO International Standard, a correlation factor of 1/1.872 will be applied to convert the reported results from NT50 titer to GMC in IU/mL which is the assigned unit for WHO International Standard. Hence, data analyses for PNA NT50 results will be expressed in IU/mL.

Anti-S IgG antibody titers will be measured by ELISA assay which detects IgG antibodies to the full-length pre-fusion Spike protein of SARS-CoV-2. According to the study endpoints, serum antibody concentration will be reported from the central laboratory in ELISA Units (ELU)/mL. A correlation factor of 1/7.9815 will be applied to convert the reported results from ELU/mL to Binding Antibody Units (BAU)/mL which is the assigned unit for WHO International Standard. Hence, data analyses for anti-S IgG results will be expressed in BAU/mL.

## Appendix 1.A. Characteristics at Screening

Tables copied from the protocol:

**Table 1: Treatment Groups - Protocol Table 3 (see [Table 1](#) in Section [4.1.](#))**

**Table 2: Phase 1 Dose Escalation Step – Protocol Table 4 (see [Table 2](#) in Section [4.1.](#))**

**Table 3: Schedule of Study Visits and Procedures – Protocol Table 5**

VISIT	Screen	V1	V2	V3	V4	V5	V6	V7
Study Day (allowed window in days)	-42 to 1	1	8 (+3)	29 (+3)	36 (+3)	43 (+3)	57 (+7)	197 (+14)
Informed consent	✓							
Demographics	✓							
Medical History	✓							
Concomitant medications A	✓	✓	✓	✓	✓	✓	✓	✓
Eligibility check	✓			~				
Vital signs	✓	✓ ^ ✓	✓	✓ ^ ✓	✓	✓	✓	✓
Complete physical exam	✓							
Targeted physical exam B		✓	✓	✓	✓	✓	✓	✓
Clinical chemistry C	✓		✓		✓			
Hematology D	✓		✓		✓			
Viral serology tests E	✓							
Urine pregnancy test F	✓	✓ ^ ✓		✓				
Unsolicited AEs G	✓	✓	✓	✓	✓	✓	✓	✓
Concomitant medications H	✓		✓	✓	✓	✓	✓	✓
Randomization		✓		~				
Blood for humoral immunity		✓		✓		✓		✓
Blood for CMI I		✓				✓		✓
Administer study product		✓		✓				
Observation/solicited AEs		✓		✓				
Provide Diary Card		✓		✓				
Review Diary Card			✓		✓			
Exit study								
Blood volumes (mL):								
Safety laboratory tests (Phase 1 only)	4		4		4			
HBV and HCV screening	2		0		0			
Humoral immunity		10		10		10		10
Cell-mediated immunity		16				16		16

~ Confirmation

A Evaluations will be conducted twice – before and after vaccinationB After Visit 6, only medications associated with an AESI, MAAE or SAE will be recorded.C Targeted PE will be conducted only in the event of new symptom, sign or, until Visit 6, any new AE; or, after Visit 6, any new AESI, MAAE or SAE.D Serum creatinine, ALT, AST, total bilirubin; only in Phase 1.E WBC count, hemoglobin, platelets; only in Phase 1.F HBsAg, HCV AbG Women of childbearing potential (WOCBP) onlyH After Visit 6, only AESI, MAAEs, and SAEs will be recorded.I After Visit 6, only concomitant medications associated with a newly reported AESI, MAAE or SAE will be recorded Only in subset of subjects in Phase 2

Remark: 1 month = 28 days (4 weeks)

